5.0 ANALYSIS ENDPOINTS

5.1 Primary Endpoint

- Change from Baseline in the CSFQ-14 total score difference for vortioxetine vs paroxetine after 5 weeks of treatment.

5.2 Secondary Endpoints

- Change from Baseline in the CSFQ-14 total score difference for vortioxetine vs paroxetine at each visit assessed.
- Change from Baseline in CSFQ-14 total score difference for paroxetine vs placebo at each visit assessed.
- Change from Baseline in CSFQ-14 total score difference for vortioxetine vs placebo at each visit assessed.
- Percentage of subjects meeting criteria for sexual dysfunction (ie, CSFQ-14 total score ≤ 47 for men and ≤ 41 for women) at any visit during the 5-week double-blind Treatment Period.
- Change from Baseline in CSFQ-14 subscales 5 dimensions (pleasure, desire/frequency, desire/interest, arousal/erection, and orgasm/ejaculation) and 3 phases of the sexual response cycle (desire, arousal, and orgasm/completion) at each visit assessed.

5.3 Additional Endpoints

- Percentage of subjects meeting criteria for sexual dysfunction (ie, CSFQ-14 total score ≤ 47 for men and ≤ 41 for women) at any 2 consecutive visits during the 5-week double-blind Treatment Period.
- Time to sexual dysfunction as assessed by the CSFQ-14.
- Percentage of subjects with a shift in the CSFQ-14 from normal (ie, CSFQ-14 total score > 47 for men and > 41 for women) at Baseline to abnormal (ie, CSFQ-14 total score ≤ 47 for men and ≤ 41 for women) at each visit assessed.
- Percentage of subjects showing decreased sexual function (ie, negative responders) according to the CSFQ-14 (ie, CSFQ-14 total score decrease from Baseline ≥ 3) at each visit assessed.
- Patient Global Impression of Improvement (PGI-I) score at each visit assessed.
- Columbia-Suicide Severity Rating Scale (C-SSRS) at each visit assessed.

5.4 Safety Assessments

- Adverse events (AEs), vital signs, clinical laboratory tests, weight, and physical examinations.

6.0 DETERMINATION OF SAMPLE SIZE

Approximately 352 male and female subjects will be randomized to 4 treatment arms. Randomization will be stratified by sex. Men and women will be enrolled in approximately equal proportions (ie, 50% men and 50% women overall).

Assuming an SD of 8.5 for the change from Baseline in CSFQ-14 total score, a total of 352 male and female subjects (88 subjects per arm) is sufficient to achieve $\geq 80\%$ power to detect a difference of 4.0 for vortioxetine 20 mg vs paroxetine 20 mg or for vortioxetine 10 mg vs paroxetine 20 mg by a 2-sample t-test with a 0.025 2-sided significance level. Given the proposed Holm-Bonferroni method (see Section 7.9.3) for multiplicity control, the power to achieve the significance for each vortioxetine dose is approximately 85%.

7.0 METHODS OF ANALYSIS AND PRESENTATION

7.1 General Considerations

7.1.1 Statistical Software

Statistical analysis will be performed using the SAS System®, Version 9.2 or greater, on a Windows platform.

7.1.2 Summary Statistics and Precision

All tabulations of analysis results will include summaries for the following treatment groups: , vortioxetine 10mg/day, vortioxetine 20mg/day, paroxetine 20 mg/day and placebo.

All confidence intervals, statistical tests, and resulting p-values will be reported as nominal 2-sided and will be assessed at the 5% significance level. No adjustments will be made for multiplicity aside from those for the primary efficacy analysis.

For continuous variables, descriptive statistics will include the number of subjects (n), mean, SD or standard error (SE), as appropriate, minimum, median, and maximum. The number of decimal places displayed for each statistic will be determined as follows:

- Mean and median: 1 more than the number of decimal places allotted in the electronic case report form (eCRF) except for the CGI scales, where 2 decimal places will be reported.
- SD and SE: 2 more than the number of decimal places allotted in the eCRF.
- Minimum and maximum: equal to the number of decimal places allotted in the eCRF.
- Confidence intervals will be presented using the same number of decimal places as the parameters (eg, mean).

For categorical data, frequency counts and percentages will be presented. Percentages will be reported to 1 decimal place.

The data summaries will be accompanied by individual subject data listings sorted by treatment, study center and subject identifier. All data available from eCRFs will be listed. The actual day relative to the start of treatment will be determined and included in the listings.

Derived analysis datasets will be produced from raw data and laboratory data. This allows for convenient reviewing of the data as well as any necessary supplemental analyses. All data from the raw datasets will be included in the derived datasets. Derived dataset specifications will be developed to include the names and definitions of derived variables in the derived SAS datasets.

7.1.3 Definition of Study Day and Study Visit Windows

A windowing convention will be used to determine the analysis value for a given study visit that applies to observed data.

Study Day -1 corresponds to the date of the Baseline visit, ie, the randomization date. Other study days are defined relative to Study Day 1, the date of first double-blind study drug dose. Relative day is calculated as (date of interest – date of first dose +1) for study days on or after the

date of first dose and as (date of interest – date of first dose) for study days prior to the first dose date.

For each visit, a window will be defined such that the lower and upper bounds of each window is generally the midpoint between 2 consecutive study visits. The visit windows and applicable study day ranges are presented below in [Table 7.a](#).

Table 7.a Visit Windows

Nominal Visit Week	Nominal Visit Day	CSFQ-14, PGI-I, C-SSRS	Vital signs	Lab, PE,Weight,	PK
Baseline	-1 (a)	≤1 (b)	≤1	≤1	≤1 (b)
1	7	2 – 10			
2	14	11 – 17	2-24		
3	21	18 – 24			2-24
4	28	25 – 31			25-31
5	35	≥32	≥25	≥2	≥32
7	49				

(a) Baseline day has been defined as Day -1 in keeping with Clinical Data Interchange Consortium standards. There is no Day 0.

(b) No baseline assessment for PGI-I or pharmacokinetic (PK) sampling.

More than 1 result for a parameter may be obtained in a visit window. In such an event, the result with the date closest to the scheduled visit day will be used. In the event of 2 observations equidistant to the scheduled visit day, the later of the observations will be used. Treatment Period Last Visit values will be defined irrespective of falling in a particular window. Hence, the windowed Week 8 value may be different than the Last Visit value.

In general, the baseline value for a variable is defined as the last observation prior to the first dose of double-blind study medication (visit date \leq first dose date), including the screening value, if necessary.

Adverse events that start more than 30 days after the last dose of double-blind study medication (start date – last dose date >30) will be listed, but excluded from the summaries and analyses. For efficacy and other safety data, data that are obtained more than 7 days after the last dose of double-blind study medication (visit date – last dose date >7) will be listed, but excluded from summaries and analyses. For certain safety measurements such as laboratory tests, summary statistics for the last visit will be presented, which will display values closest to the last dose of the double-blind medication within the cutoff day for that variable.

If the date of the first double-blind dose is missing due to the subject being lost to follow-up after being dispensed drug then the first dose dispensed date + 1 day will be used for analysis and summary purposes. Similarly, if the date of last double-blind dose is missing, then the date of the last double-blind drug dispense date + (the last number of doses dispensed – the last number of doses returned) - 1 will be used.

The study window convention will not be applied to the eCRF data listings. The data listings for eCRF data will display the raw data as collected and entered in the eCRF. For CSFQ-14 and PGI-I, windowed visits will be shown on the listings.

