7.4 Criteria for Discontinuation or Withdrawal of a Subject

The primary reason for discontinuation or withdrawal of the subject from the study or study drug should be recorded in the electronic case report form (eCRF) using the following categories. For screen failure subjects, refer to Section 9.1.17.

1. Pretreatment event (PTE) or AE. The subject has experienced a PTE or AE that requires ET because continued participation imposes an unacceptable risk to the subject's health or the subject is unwilling to continue because of the PTE or AE.
 - Liver Function Test (LFT) Abnormalities
Study drug should be discontinued immediately with appropriate clinical follow-up (including repeat laboratory tests, until a subject's laboratory profile has returned to normal/baseline status, see Section 9.1.12), if the following circumstances occur at any time during study drug treatment:
 - ALT or AST $>8\times$ ULN, or
 - ALT or AST $>5\times$ ULN and persists for >2 weeks, or
 - ALT or AST $>3\times$ ULN in conjunction with elevated total bilirubin $>2\times$ ULN or international normalized ratio (INR) >1.5 , or
 - ALT or AST $>3\times$ ULN with appearance of fatigue, nausea, vomiting, right upper quadrant pain or tenderness, fever, rash, and/or eosinophilia ($>5\%$).
2. Significant protocol deviation. The discovery postrandomization that the subject failed to meet protocol entry criteria or did not adhere to protocol requirements, and continued participation poses an unacceptable risk to the subject's health.

3. Lost to follow-up. The subject did not return to the clinic and attempts to contact the subject were unsuccessful. Attempts to contact the subject must be documented in the subject's source documents.
4. Voluntary withdrawal. The subject wishes to withdraw from the study. The reason for withdrawal, if provided, should be recorded in the eCRF.

Note: All attempts should be made to determine the underlying reason for the withdrawal and, where possible, the primary underlying reason should be recorded (ie, withdrawal due to an AE should not be recorded in the "voluntary withdrawal" category).

5. Study termination. The sponsor, IRB, or regulatory agency terminates the study.
6. Pregnancy. The subject is found to be pregnant.

Note: If the subject is found to be pregnant, the subject must be withdrawn immediately. The procedure is described in Section [9.1.14](#).

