Beta hCG (for pregnancy) (a)	Beta hCG (for pregnancy) (g)

GGT=γ-glutamyl transferase, hCG=human chorionic gonadotropin, RBC=red blood cell, WBC=white blood cell.

(a) To be performed at Screening only.

(b) To be performed only if total bilirubin ≥ 2 mg/dL.

(c) Microscopic examination of sediment to be performed only if the dipstick results are positive.

(d) To be performed only if subjects experience ALT or AST $>3 \times$ ULN as part of the required follow-up laboratory tests.

(e) TSH to be measured at Screening to exclude subjects with clinically significant thyroid dysfunction

(hyperthyroidism or hypothyroidism), which may impact sexual functioning. If TSH value is outside the normal range, free T4 will be measured.

(f) To be performed at Screening, Baseline, and at any time at the discretion of the investigator.

(g) To be performed at all study visits except Screening.

The central laboratory will perform all clinical laboratory tests with the exception of the urine pregnancy (hCG) tests, which will be performed at the study site. The clinical laboratory test results will be returned to the investigator, who will be responsible for filing and reviewing these

results together with the data in the eCRF. The investigator is responsible for recording the interpretation of clinical significance of any abnormal laboratory results in the eCRF. The investigator will maintain a copy of the laboratory accreditation and the reference ranges for the laboratory used.

If subjects experience ALT or AST $>3\times\text{ULN}$, follow-up laboratory tests (at a minimum, serum alkaline phosphatase, ALT, AST, total bilirubin, GGT, and INR) should be performed within a maximum of 7 days and preferably within 48 to 72 hours after the abnormality was noted.

(Please refer to Section 7.4 for discontinuation criteria, and Section 10.1.5.2 for the appropriate guidance on reporting of abnormal LFTs in relation to ALT or AST $>3\times\text{ULN}$ in conjunction with total bilirubin $>2\times\text{ULN}$.)

If the ALT or AST remains elevated $>3\times\text{ULN}$ on these 2 consecutive occasions the investigator must contact the medical monitor for consideration of additional testing, close monitoring, possible discontinuation of study drug, and discussion of the relevant subject details and possible alternative etiologies. The abnormality should be recorded as an AE (please refer to Section 10.2.3 for reporting requirements).

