7.10 Analyses of Columbia-Suicide Severity Rating Scale (C-SSRS)

The following summaries will be presented for C-SSRS scale in the safety analysis set:

- Descriptive statistics by study visit.
- Number of subjects with positive reports at baseline and during treatment.
- A shift-table to demonstrate changes from baseline in C-SSRS scores during treatment.

A subject with a positive report at baseline if the subject reported any of the following suicidal ideation or behavior:

- Active suicidal ideation with some intent to act, without specific plan.
- Active suicidal ideation with specific plan and intent.
- Any actual suicide attempt.
- Any interrupted suicide attempt.
- Any aborted suicide attempt.
- Any preparatory acts or behavior.

A subject with a positive report during treatment if the subject reported any of the following suicidal ideation or behavior:

- Active suicidal ideation with some intent to act, without specific plan.
- Active suicidal ideation with specific plan and intent.
- Any actual suicide attempt.
- Any interrupted suicide attempt.
- Any aborted suicide attempt.
- Any preparatory acts or behavior.
- Completed suicide.

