7.13.1 Adverse Events

All adverse events will be coded using MedDRA version 19.0. In this dictionary, each verbatim term is coded to a lower level term, and then mapped to a preferred MedDRA term, which is then

mapped to an SOC. All adverse events will be included in the data listings but only treatment-emergent adverse events will be included in the summary tables.

A treatment-emergent adverse event (TEAE) is defined as an adverse event with an onset that occurs after receiving study drug (AE start date \geq first dose date) and within 30 days after receiving the last dose of study drug (AE start date – last dose date \leq 30). A TEAE may also be a pretreatment adverse event or a concurrent medical condition diagnosed prior to the date of first dose of study drug that increases in severity after the start of dosing. Adverse events data with onset occurring more than 30 days after last dose of study drug (AE start date – last dose date $>$ 30) will be listed, but not included in the summary tables. Adverse events with missing onset dates will be summarized regardless of severity and relationship to study medication.

Serious adverse events (SAEs) with onset that occurs after receiving study drug (AE start date \geq first dose date) and within 30 days after receiving the last dose of study drug (AE start date - last dose date \leq 30) will be summarized.

In the high-level adverse event summary tables, TEAEs will be summarized regardless of intensity and relationship to study drug. Within each subject, multiple reports of events that map to a common MedDRA term will be counted only once.

At the adverse event level, the summary tables will present the number of subjects reporting each of these MedDRA events, ie, the number of subjects reporting 1 or more events that map to the given MedDRA term.

At the SOC level, the summary tables will present the number of subjects reporting 1 or more events that map to the given SOC. That is, the number of subjects reported at the SOC level will be less than or equal to the sum of the subject counts across all adverse events within that SOC.

In selected summaries (TEAEs overview, and TEAEs by SOC and preferred term), adverse events will be summarized by the number of events reported in addition to the number and percentage of subjects with events.

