7.13.3 Liver Function Tests

Liver function tests will be summarized by visit. Number and percentage of subjects who meet liver function test criteria will be summarized by treatment.

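### The SAP's 7-day cut-off can take an early stopper's only post-baseline laboratory sample, or a late bilirubin or INR finding, out of the safety incidence counts

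*SAP*

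**What the plan says.** SAP 7.1.3 sets two post-dose limits. Adverse events are summarised if they start "within 30 days after receiving the last dose of study drug" (wording from SAP 7.13.1). Everything else has a shorter limit: "For efficacy and other safety data, data that are obtained more than 7 days after the last dose of double-blind study medication" "will be listed, but excluded from summaries and analyses". The last-visit laboratory summary is bound by the same limit: it gives summary statistics "which will display values closest to the last dose of the double-blind medication within the cutoff day for that variable".

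The tables affected make no exception. SAP 7.13 refers back to 7.1.3 for its conventions. SAP 7.13.2 counts subjects with any post-baseline PCS laboratory value. SAP 7.13.3 says "Number and percentage of subjects who meet liver function test criteria will be summarized by treatment" and does not name the criteria. SAP 7.10 counts "Number of subjects with positive reports at baseline and during treatment".

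On the protocol side, Appendix A schedules one post-baseline chemistry and haematology sample, at Week 5/ET. Sections 7.5 and Appendix A footnote (a) ask for the ET procedures in subjects who leave early, without a deadline counted from last dose. After an ALT or AST above 3×ULN, section 9.1.12 says follow-up tests "should be performed within a maximum of 7 days and preferably within 48 to 72 hours after the abnormality was noted". Table 9.b shows that INR is measured only in that follow-up panel.

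**The concern.** The cut-off runs from last dose, but two kinds of protocol-required safety data do not. The ET visit happens whenever the subject comes back. The liver retest clock starts when the abnormality is noted, which is after the laboratory has reported. Either can fall past day 7.

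For an early terminator the ET sample is the only scheduled post-baseline laboratory result. If it is excluded, the subject contributes nothing to the PCS or liver counts but may still sit in the safety set as someone without an abnormality. People who stop early, or who have a liver signal, are the ones a safety table most needs to hold. One subject in an arm of 88 is 1/88 = 1.1 percentage points, which is visible in a table of uncommon events.

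**Working it through.** The plan has no figure of its own to reproduce here; the check is date arithmetic against the rule that a value is excluded when visit date − last dose date > 7.

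**1. Late ET visit.** Inputs: weekly visits with a ±3-day window (Protocol Appendix A), so the Week 2 visit falls on Days 11 to 17. Example: last dose on Day 8, the day after a Day 7 visit.

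| Return day | Days after last dose | Result |
|---|---|---|
| 14 | 14 − 8 = 6 | kept |
| 15 | 15 − 8 = 7 | kept |
| 16 | 16 − 8 = 8 | excluded |
| 17 | 17 − 8 = 9 | excluded |

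More generally, let the subject stop *s* days after the last attended visit and return at the late edge of the next window, 7 + 3 = 10 days after that visit. Time off drug is 10 − *s*: 10, 9 and 8 days for *s* = 0, 1 and 2 (excluded), and 7 days for *s* = 3 (kept). A return on the nominal day gives 7 − *s*, which is never more than 7. So the next weekly visit is lost only if the stop is early in the interval and the return is late in the window. Returning one visit later makes loss more likely: with *s* = 0 the time off drug is 11 to 17 days.

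**2. Liver retest after a Week 5 elevation.** Days after last dose = (draw − last dose) + (draw to result noted) + (noted to retest). The retest interval of 2, 3 or 7 days is from Protocol 9.1.12. A draw at 0 or 1 day and a turnaround of 0 to 3 days are assumptions.

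- Retest at 48 to 72 hours: from 0 + 0 + 2 = 2 to 1 + 3 + 3 = 7 days. All 16 combinations are kept.
- Retest at 7 days: from 0 + 0 + 7 = 7 to 1 + 3 + 7 = 11 days. Excluded in 7 of 8 combinations; kept only with a same-day draw and a same-day result.

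**3. What a lost retest changes.** The retest trigger is ALT or AST above 3×ULN (Protocol 9.1.12). The PCS threshold is at or above 3×ULN (SAP Appendix B). The Week 5 sample that triggers the retest is therefore already a PCS case, and it is kept at 0 to 1 day after last dose. Total bilirubin is on the same Week 5 panel. Only a new finding can be lost:

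- bilirubin that first reaches its own PCS limit (2.0 mg/dL) in the late retest;
- an abnormal INR, which has no Week 5 value. INR is not in the SAP 7.13.2 list or in Appendix B, so it matters only if the undefined 7.13.3 criteria use it.

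**4. C-SSRS.** It is done at every visit to Week 5/ET, and the Week 7 contact is by telephone without it. Only the C-SSRS at a late ET visit is lost; earlier weekly assessments remain.

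**The case against.** A short on-treatment window for laboratory values beside a longer one for adverse events is a common and coherent choice, and no bias between arms has been shown. Excluded values stay in the listings, where out-of-range and PCS results are flagged. Missed doses alert the site (Protocol 9.2), which makes long unnoticed gaps less likely. All of this stands, and it keeps the point small.

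Four stronger readings are tempting, and the documents do not support them.

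- *Confirmed liver signals vanish.* They do not. The Week 5 index value is counted, and ALT or AST above 3×ULN on two consecutive occasions is recorded as an adverse event. With bilirubin above 2×ULN and no other cause found it is a serious one (Protocol 10.2.3). Both are summarised up to 30 days after last dose. The open-ended testing in Protocol 7.4, until the "laboratory profile has returned to normal/baseline status", concerns subjects who have already met a criterion.
- *The more-than-2-week persistence criterion can never be counted.* That criterion in Protocol 7.4 is a rule for stopping study drug and applies only while the subject is on it. SAP 7.13.3 does not say that it tabulates the 7.4 criteria.
- *A suicide attempt after Week 5 is missing from the C-SSRS table because of the cut-off.* For completers no later C-SSRS is scheduled, so no cut-off would bring it in. An attempt is an SAE (Protocol 10.1.3) and falls under the 30-day limit. The SAP 7.10 count is also labelled as a during-treatment count, which partly fits leaving out off-drug reports.
- *The counts are understated.* They can be; nothing in the documents shows that they will be.

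The objection does not answer the late ET visit. There, no index value exists to fall back on, and an abnormal laboratory value that the investigator does not judge clinically significant never becomes an adverse event (Protocol 10.1.3).

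**Conclusion.** The point holds in limited form. The 7-day rule can remove an early terminator's only scheduled post-baseline laboratory sample, and that visit's C-SSRS, from the incidence counts. It can also remove a bilirubin or INR abnormality first seen in a liver retest near the permitted 7-day limit. PCS and liver-criteria counts can then be too low; the C-SSRS count is touched only through late ET visits.

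The number affected is probably small and cannot be computed, because the documents give no rate of early stopping, late return or liver elevation. The retest result rests on the assumed draw and turnaround times. The INR part rests on SAP 7.13.3 using INR at all. Efficacy and by-visit summaries are not in question.

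**What to change.** In SAP 7.1.3, keep the 7-day cut-off for efficacy and by-visit means. Add that subject-level incidence of PCS laboratory values and of the 7.13.3 liver criteria uses all post-baseline values, scheduled or unscheduled, up to 30 days after last dose, the window already used for adverse events. Flag values more than 7 days after last dose as off-treatment. Show C-SSRS reports from late ET visits on a separate line from the during-treatment count in 7.10. State in 7.13.3 which liver criteria are counted and whether INR is among them; without that the count cannot be programmed in one agreed way.

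Every retest in the grid above (at most 11 days) and the late ET example (8 to 9 days) would then be included. The cost is a few SAP sentences and a programming flag on data already collected, with no change to visits or subject care. The downside is that some off-drug values enter the incidence counts; the flag lets a reader separate them.
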